9.1.2. Rechallenge

Resumption of study treatment after temporary discontinuation should always be discussed with the medical monitor.

9.2. Discontinuation from the Study

- A participant may withdraw from the study at any time at his/her own request, or may be withdrawn at any time at the discretion of the investigator for safety, behavioural, or administrative reason.
- If the participant withdraws consent for disclosure of future information, the sponsor may retain and continue to use any data collected before such a withdrawal of consent.
- If a participant withdraws from the study, he/she may request destruction of any samples taken and not tested, and the investigator must document this in the site study records.
- Refer to the SoA for data to be collected at the time of study discontinuation and follow-up and for any further evaluations that need to be completed.

9.3. Lost to Follow-Up

A participant will be considered lost to follow-up if he or she repeatedly fails to return for scheduled visits and is unable to be contacted by the study site.

The following actions must be taken if a participant fails to return to the clinic for a required study visit:

- The site must attempt to contact the participant and reschedule the missed visit as soon as possible and counsel the participant on the importance of maintaining the assigned visit schedule and ascertain whether or not the participant wishes to and/or should continue in the study.
- In cases in which the participant is deemed lost to follow-up, the investigator or designee must make every effort to regain contact with the participant (where possible, 3 telephone calls and, if necessary, a certified letter to the participant's last known mailing address or local equivalent methods). These contact attempts should be documented in the participant's medical record.
- Should the participant continue to be unreachable, he/she will be considered to have withdrawn from the study with a primary reason of lost to follow-up.

10. Study Assessments and Procedures

Study procedures and their timing are summarised in the [SoA](#).

- Adherence to the study design requirements, including those specified in the SoA, is essential and required for study conduct.
- All screening evaluations must be completed and reviewed to confirm that potential participants meet all eligibility criteria. The investigator will maintain a screening log to record details of all participants screened and to confirm eligibility or record reasons for screening failure, as applicable.
- The maximum amount of blood collected from each participant over the duration of the study, including any extra assessments that may be required, will not exceed 480 mL over the duration of the study.
- Repeat or unscheduled samples may be taken for safety reasons or for technical issues with the samples.

10.1. Efficacy Assessments

10.1.1. Radiology

In order to ensure the consistent assessment of BMD and fractures, site-based radiology staff and central readers will be fully trained. Details of each radiological assessment, procedures for calibration of equipment to ensure assessment continuity and central reading procedures will be provided in the MBPS205 Imaging Charter and Training Manual and made available.

10.1.1.1. HRpQCT

HRpQCT scans, including calibration, should be performed according to MBPS205 Imaging Charter and Training Manual on distal non-dominant arms unless the arm has been supported with rods or there is significant deformity. In this case, the investigator should document that the dominant limb was selected and specify the rationale. If rodding (or other metal implant) is present in both distal tibiae, or if severe deformities do not physically allow entry of either lower limb into the HRpQCT scanner, please discuss the participant's involvement in the study with the study medical monitor prior to inclusion in the study.

HRpQCT will be used to measure the primary efficacy endpoint of trabecular volumetric BMD of the radius (see [SoA](#)).

In addition, HRpQCT will be used to examine other aspects of the tibial and radial trabecular and cortical bone volume and microarchitecture. Morphological analysis will measure or derive bone volume, trabecular number, thickness and spacing, cortical volume and thickness, structure model index, connectivity density and degree of anisotropy.

Exploratory end points will be assessed with time-lapse dynamic in vivo morphometry of HRpQCT image datasets.

Morphological analysis procedures are described in detail by ([Liu et al 2010](#)) and in the MBPS205 Imaging Charter and Manual.

Refer to [Appendix 6](#) for Radiation Exposure.

10.1.1.2. Dual-Energy X-ray Absorptiometry

Bone mineral density will also be evaluated using DXA. T-Score will be calculated based on actual measured bone density value. Change in TBS from baseline will be assessed from DXA images using TBS (iNsight software). Lean and fat body mass will be evaluated using whole body DXA. Calcium tablets should not be taken 2 hours prior to DXA lumbar scan.

Refer to Appendix 6 for Radiation Exposure and the MBPS205 Imaging Charter and Imaging Training Manual for further details of the DXA including patient positioning.

10.1.1.3. Radiography

Vertebral radiographs will be used to assess the number of historic vertebral fractures, the percentage change in numbers of vertebral fractures from baseline at 6 and 12 months and the percentage change in vertebral height from baseline.

Genant's semi-quantitative method and 6-point quantitative morphometry will be used to evaluate vertebral fractures and vertebral height, as detailed in the Imaging Charter.

Fracture assessment, confirmed by central radiographic reading, will be carried out separately for peripheral including all major long bones, minor bone (digits, ribs) and vertebral fractures. Fractures without clinical symptoms, detected only by means of radiographic investigations will not be included in the analysis.

Date of diagnosis (defined as first occurrence of symptoms of fracture) will be adopted for all time to event analyses.

Refer to [Appendix 6](#) for Radiation Exposure and the MBPS205 Imaging Charter and Manual for further details.

10.1.2. Bone Biopsy

Bone biopsies will be performed once at either Month 6 or Month 12 in a sub-set of participants. Informed consent will be obtained using a specific bone biopsy consent form.

Double labelling of bone, according to the procedure detailed in the MBPS205 Bone Biopsy Manual, will be carried out before the bone biopsy procedure to allow determination of the level of bone turnover, and bone formation and mineralisation rates.

All biopsies will be analysed at a central laboratory as per the MBPS205 Bone Biopsy Manual.

10.1.3. Audiometry

This procedure can be omitted if the investigative site does not have the capability to complete the audiometry assessment. Participants will be asked to remove anything which might affect the test results such as spectacles, earrings and hearing aids. The ear will be examined with an otoscope to assess the requirement for wax removal and to determine whether the eardrum has suffered any damage which may reduce the ability of sound to be transported to the cochlea. The audiometric test will be carried out using standard or automatic audiometers. The participant will be asked to indicate whether they can just hear or cannot hear a certain sound; the sound level may be increased from a very low level or reduced from a high level. Headphones will be fitted to the participant and the test performed on each ear. A threshold test will be performed first in which each ear will be subjected to sound at a frequency of 1 kHz at varying levels of intensity ranging from low to high and high to low. This will be repeated several times in order to derive an average threshold for the test. Following this pre-check, both of the participant's ears will be tested through a range of frequencies (0.5, 1, 2, 3, 4, 6 and 8 kHz) and hearing loss recorded for each frequency via a series of sound exposures. The decibel hearing loss will be recorded using the grading scores in [Appendix 7](#).

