Appendix 7: Audiometry Scale

Grade on audiometry (db loss)	Score
<21	undetectable hearing loss
21-35	mild
36-60	moderate
>60	severe

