4.3 Exploratory endpoints

The exploratory endpoints of this study are:

1. Changes in Trabecular Bone Score (TBS) from baseline at 6 and 12 months
2. Changes in usage or need for physical aids from baseline at 12 months
3. Change in auditory function from baseline at 12 months in a subset of patients
4. Change in bone formation from baseline at 6 and 12 months, including:

-
- Normalised newly mineralised bone volume (MV/BV)
 - Normalised newly mineralised surface area (MS/BS)
 - Mineralised thickness (MTh)
 - Normalised formation patch number density (N.F. Patch/BV)
 - Formation patch volume (F.PatchVol.)
 - 3D bone formation rate (3D BFR/BS)
 - 3D mineral apposition rate (3D MAR)
5. Change in bone resorption from baseline at 6 and 12 months, including:
- Normalised newly eroded bone volume (EV/BV)
 - Normalised newly eroded surface area (ES/BS)
 - Erosion depth (ED)
 - Normalised resorption cavity number density (N.R.Cav./BV)
 - Resorption cavity volume (R.Cav.Vol.)
 - 3D bone resorption rate (3D BRR/BS)
 - 3D mineral resorption rates (3D MRR)

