8.5.4.2 Auditory Function

The audiometry score (Undetectable hearing loss, mild, moderate or severe) at each visit will be summarised descriptively by ear and treatment group.

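### The hearing endpoint is change from baseline, but the SAP summarises only a four-level grade at each visit, with no within-person change, no use of the decibel values and no rule for combining seven frequencies

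*Protocol*

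**What the plan says.** SAP 4.3 lists as an exploratory endpoint "Change in auditory function from baseline at 12 months in a subset of patients". The Protocol objectives table has the same endpoint at the tertiary/exploratory level.

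Protocol 10.1.3 describes the test. After a 1 kHz pre-check, both ears are to be "tested through a range of frequencies (0.5, 1, 2, 3, 4, 6 and 8 kHz) and hearing loss recorded for each frequency". The next sentence reads "The decibel hearing loss will be recorded using the grading scores in" Appendix 7. That appendix has four levels by decibel loss: below 21 ("undetectable hearing loss"), 21-35 (mild), 36-60 (moderate) and above 60 (severe).

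The treatment-period Schedule of Activities places audiometry at screening and at Month 12/EOT only. Section 10.1.3 also allows that "This procedure can be omitted if the investigative site does not have the capability to complete the audiometry assessment".

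The whole planned analysis is one sentence in SAP 8.5.4.2: "The audiometry score (Undetectable hearing loss, mild, moderate or severe) at each visit will be summarised descriptively by ear and treatment group".

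**The concern.** The endpoint is a change within a person. The planned output is a set of grade counts at each visit. Three gaps follow.

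- **Change.** Counts at two visits do not show who moved, and opposite moves cancel.
- **Resolution.** The test produces decibel thresholds, but no summary of them is planned. Worsening inside a grade does not show, while a small shift over a cut-point shows as a full step.
- **Derivation.** The SAP reports a grade by ear, yet neither document says whether it comes from an average, from selected frequencies, from the worst frequency, or is given separately at each frequency.

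At stake is whether the hearing tables can describe the quantity that the endpoint names. Protocol 4.1 lists hearing loss among the features of osteogenesis imperfecta, and Protocol 10.1.4 counts it among the areas covered by the OIQoL-A.

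**Working it through.** The documents give no sample size, power or effect size for hearing, so there is no plan figure to reproduce. The check applies the Appendix 7 cut-points.

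**Inputs.** Grade as a function of decibel loss x: undetectable if x < 21; mild if 21 ≤ x ≤ 35; moderate if 36 ≤ x ≤ 60; severe if x > 60. Seven frequencies per ear (Protocol 10.1.3). Two assessments (Schedule of Activities).

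**Largest worsening with no change of grade** = highest value in the grade − lowest value in the grade.

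| Grade | Whole-dB readings | 5 dB steps (assumption) |
|---|---|---|
| Undetectable, if the floor is 0 dB (assumption) | 20 − 0 = 20 | 20 − 0 = 20 |
| Undetectable, if the floor is −10 dB (assumption) | 20 − (−10) = 30 | 20 − (−10) = 30 |
| Mild | 35 − 21 = 14 | 35 − 25 = 10 |
| Moderate | 60 − 36 = 24 | 60 − 40 = 20 |
| Severe, if the audiometer stops at 90, 100 or 120 dB (assumption) | 29, 39 or 59 | 25, 35 or 55 |

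Only the mild and moderate grades have both ends fixed by Appendix 7. The documents set no upper limit for the severe grade and no floor for the lowest.

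**Smallest worsening that changes the grade.** In whole dB it is 1 dB (20 to 21, 35 to 36, 60 to 61). In 5 dB steps it is 5 dB (20 to 25, 35 to 40, 60 to 65).

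**Visit counts against change.** Take two ears in one arm. One goes from mild to moderate and the other from moderate to mild. Each visit shows one mild and one moderate ear, so the two summaries are identical although both ears moved.

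**Effect of the missing derivation rule.** Take a hypothetical ear with losses of 15, 15, 15, 20, 30, 50 and 65 dB from 0.5 to 8 kHz.

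- Mean of all seven: (15 + 15 + 15 + 20 + 30 + 50 + 65)/7 = 210/7 = 30, mild.
- Mean of 0.5, 1 and 2 kHz: 45/3 = 15, undetectable.
- Worst frequency: 65, severe.

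One audiogram gives three different grades, depending on a rule that is not stated.

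**Comparison within the SAP.** The other exploratory measures with their own subsection in 8.5.4 (trabecular bone score, bone formation, bone resorption) each have an ANCOVA of change from baseline. Vertebral fracture grade, also an ordered scale, has a shift table from worst baseline to worst post-baseline grade (8.5.3.3.1). Hearing has neither.

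**The case against.** The strongest reply is that the plan covers more than 8.5.4.2 shows. Protocol 11.3.3 sends exploratory endpoints to the general methods, and Protocol 11.3 says that changes from baseline will be summarised for efficacy data. SAP 8.1.8 puts the relevant patient data in individual listings, so grades at the two visits can be paired by hand. This stands in part: the protocol intends some summary of change. But the SAP section written for hearing does not carry that through, and neither the general text nor the listings say that decibel values will be summarised or how the grade is formed.

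It can also be said that clinical severity grades are a legitimate choice for a descriptive exploratory endpoint. That is fair, and it limits the priority. It does not supply the missing change or the missing rule.

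Three stronger readings are tempting, and the documents do not support them.

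- A reader might infer that hearing is recorded only as grades. Protocol 10.1.3 says first that loss is recorded for each frequency and then that it is recorded with the grades. The eCRF is not shown, so decibel fields may exist.
- A reader might infer that each ear's seven results become one value. The SAP says by ear, not one score per ear, and Appendix 7 could be applied at each frequency. The documents are silent.
- A reader might infer that the trial would report no effect on hearing whatever happened. No test or claim on hearing is planned, and worsening across a grade boundary could still appear.

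**Conclusion.** The point holds as a gap in the analysis specification. SAP 8.5.4.2 does not deliver the change that the endpoint names, leaves the decibel measurements out of the summaries, and gives no rule from seven frequencies to a grade.

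The blind range is 14 dB in the mild grade and 24 dB in the moderate grade in whole decibels, or 10 and 20 dB if readings are in 5 dB steps; the documents give no step size. The 24 dB figure is not an overall maximum, because the severe grade is open-ended.

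Priority is low. The endpoint is exploratory, untested and measured in a subset. It plays no part in the sample size or the primary analysis, and Protocol 6.5 bases dose selection on HRpQCT and safety.

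**What to change.** **Protocol 10.1.3:** state that the decibel threshold for each ear and frequency is captured in the eCRF. This settles the two adjoining sentences.

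**SAP 8.5.4.2:**

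1. Summarise the change in decibels from baseline to Month 12 per ear and treatment group, at each frequency and as the mean over the seven tested frequencies. The by-frequency summary guards against an average hiding a loss at a few frequencies.
2. Derive the Appendix 7 grade from that seven-frequency mean and present it as a baseline-to-Month-12 shift table by ear and treatment group. State a rounding rule, because a mean such as 35.5 falls between the mild and moderate bands as printed.
3. Keep the summary descriptive. A model with patient as a random factor for the two ears would match the SAP 8.5.1 convention for nested observations, but it is optional.

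**Cost:** some extra data fields and one or two tables, with no new procedure. Decibel values may not be retrievable for patients already tested, so the number of ears with decibel data at both visits should be reported.

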10.1.4. Patient-Reported Quality of Life

The SF-12 is a generic, 12-item survey that measures 8 domains of health: physical functioning, role limitations due to physical health, bodily pain, general health perceptions, vitality, social functioning, role limitations due to emotional problems, and mental health. It yields scale scores for each of these 8 domains and 2 summary measures of physical and mental health: The Physical Component Summary and the Mental Component Summary.

The EQ-5D-5L is a standardised measure of health status comprised of a descriptive system of 5 health-related quality of life states (i.e., mobility, self-care, usual activities, pain/discomfort, and anxiety/depression) and a Visual Analogue Scale (VAS) of overall health. Each dimension is rated on a 5-point response scale indicating severity of problems, where 1 is "no problems" and 5 is "extreme problems". The 5 questions are scored and together contribute to the EQ-5D index (utility) score between 0 and 1 (1 being perfect health), which will be calculated using the developers' algorithm based on country-specific reference score sets. The EQ-5D VAS is a measure of overall self-rated health status, used and analysed separately from the index score. The VAS ranges from 0 to 100, with higher scores indicative of better overall health.

The OIQoL-A is a PRO instrument for use in adults with OI Type I, III, or IV. The OIQoL-A currently measures 5 areas of quality of life related to OI (Physical Function, Pain, Hearing Loss, taking care/Concerns, Social and Family Life and Activities); data collected from the phase 2b trial will be used to validate the instrument prior to its use within the phase 3 study.

10.2. Adverse Events

The definitions of an AE or SAE/AESI can be found in [Appendix 4](#).

AE will be reported by the participant (or, when appropriate, by a caregiver, surrogate, or the participant's legally authorised representative).

The investigator and any designees are responsible for detecting, documenting, and reporting events that meet the definition of an AE or SAE/AESI and remain responsible for following up AE that are serious, considered related to the study treatment or the study, or that caused the participant to discontinue the study treatment (see [Section 8.7](#)).

10.2.1. Time Period and Frequency for Collecting AE and SAE/AESI Information

All AE and SAE/AESI will be collected from the signing of the ICF until the follow-up visit at the time points specified in the SoA ([Section 2](#)).

Medical occurrences that begin before the start of study treatment but after obtaining informed consent will be recorded on the Medical History/Current Medical Conditions section of the eCRF.

All SAEs/AESIs will be recorded and reported to the sponsor or designee within 24 hours, as indicated in [Appendix 4](#). The investigator will submit any updated SAE/AESI data to the sponsor within 24 hours of it being available.

Investigators are not obligated to actively seek AE or SAE/AESI in former study participants. However, if the investigator learns of any SAE/AESI, including a death, at any time after a participant has been discharged from the study, and he/she considers the event to be reasonably related to the study treatment or study participation, the investigator must promptly notify the sponsor.

The method of recording, evaluating, and assessing causality of AE and SAE/AESI and the procedures for completing and transmitting SAE/AESI reports are provided in [Appendix 4](#).

10.2.2. Method of Detecting AE and SAE/AESI

Care will be taken not to introduce bias when detecting AE and/or SAE/AESI. Open-ended and non-leading verbal questioning of the participant is the preferred method to inquire about AE occurrence.

10.2.3. Follow-up of AE and SAE/AESI

After the initial AE/SAE/AESI report, the investigator is required to proactively follow each participant at subsequent visits/contacts. All SAEs/AESIs, will be followed until resolution, stabilisation, until the event is otherwise explained, or the participant is lost to follow-up (as defined in [Section 9.3](#)). Further information on follow-up procedures is given in [Appendix 4](#).

10.2.4. Regulatory Reporting Requirements for SAE

- Prompt notification by the investigator to the sponsor of SAE is essential so that legal obligations and ethical responsibilities towards the safety of participants and the safety of a study treatment under clinical investigation are met.
- The sponsor has a legal responsibility to notify both the local regulatory authority and other regulatory agencies about the safety of a study treatment under clinical investigation. The sponsor will comply with country-specific regulatory requirements relating to safety reporting to the regulatory authority, Institutional Review Boards (IRB)/Independent Ethics Committees (IEC), and investigators.
- Investigator safety reports must be prepared for suspected unexpected serious adverse reactions (SUSAR) according to local regulatory requirements and sponsor policy and forwarded to investigators as necessary.
- An investigator who receives an investigator safety report describing an SAE or other specific safety information (eg, summary or listing of SAE) from the sponsor will file it along with the IB and will notify the IRB/IEC, if appropriate according to local requirements.

10.2.5. Pregnancy

Details of all pregnancies in female participants and female partners of male participants will be collected after the start of study treatment and until 70 days after the last dose.

If a pregnancy is reported, the investigator should inform the Safety Clinical Research Organisation (CRO) within 24 hours of learning of the pregnancy and should follow the procedures outlined in [Appendix 5](#).

Abnormal pregnancy outcomes (eg, spontaneous abortion, fetal death, stillbirth, congenital anomalies, ectopic pregnancy) are considered SAE.

10.3. Treatment of Overdose

For this study, any dose of setrusumab greater than 120% of the calculated dosage will be considered an overdose.

Mereo does not recommend specific treatment for an overdose.

In the event of an overdose, the pharmacist / unblinded CRA should:

1. Contact the ICON Medical Monitor immediately.
2. Closely monitor the participant for AE/SAE/AESI and laboratory abnormalities until setrusumab can no longer be detected systemically (at least 60 days).
3. Obtain a plasma sample for PK analysis within 14 days from the date of the last dose of study treatment if requested by the medical monitor (determined on a case-by-case basis).
4. Document the quantity of the excess dose as well as the duration of the overdosing in the eCRF and source documents.

Decisions regarding dose interruptions or modifications will be made by the investigator in consultation with the medical monitor based on the clinical evaluation of the participant.

